### F. Interventions and Interactions

Although frequent in-person sessions for nutrition education and lifestyle change counseling are typically part of glycemic control and weight loss interventions, our unique patient population does not allow for a traditional "intensive lifestyle intervention" (recovery from delivery, infant child at home, frequent newborn doctor visits). Accordingly, we focus on meal delivery as the main intervention component, coupled with the provision of nutrition and lifestyle information to increase the knowledge base and build a foundation for further improvements in lifestyle behaviors after the 3-month post-partum period in both treatment groups. Participants in both treatment groups will receive an educational email each week (unless there is a scheduled phone visit with the study team) with resources for women postpartum. These emails will include short informational videos, developed as part of a community-based translation of the **Diabetes Prevention Program (HELP** PD, IRB00000613), that contain core content on the physiological, emotional, cognitive, and behavioral basics of losing weight as well as adopting and

#### **Table 2. Outline of Monthly Phone Contacts**

1 4010	e outline of filonomy i ne		
Month	Topic and Progress Check	Research Study	Health-related Goal Setting
Month One	
 
General Check In- Self Care:
 
Sharing the importance of self-care and ideas for self-care activities
 
How are you prioritizing self-care?
 
"Goods and Bads" exercise for self-care
 
Encourage to attend 6 week postpartum visit 
 
Help with concerns about healing body
 
Ideas for contraception
 
Help with breastfeeding or feeding concerns
 
General health help and advice
 
 
 
	
 
Meal delivery (MTM group only)
 
Meal prep (MTM group only)
 
Weekly videos from study team
 
Problems with digital scale / tips on weighing
 
Other feedback
 
	
 
SMART goal setting
 
Help participant set a modest goal for self-care
 

Month Two	
 
General Check In- Dietary Awareness:
 
Brief primer on label reading (food label exercise)
 
Practice with food labels
 
Encourage to teach other family members (esp. those that do shopping)
 
	
 
Meal delivery (MTM group only)
 
Meal prep (MTM group only)
 
Weekly videos from study team
 
Self-weighing on digital scale
 
Other feedback
 
	
 
SMART goal setting
 
Help participant set a modest goal for dietary habit change
 
Eat breakfast
 
Try to notice when I am hungry
 
Have a healthy snack option in the house
 
Practice label reading
 

Month Three	
 
General Check In- Physical Activity:
 
Brief primer on walking for exercise
 
Discuss what they have liked and not liked about exercise in the past?
 
What are their current barriers to exercising?
 
	
 
Meal delivery (MTM group only)
 
Meal prep (MTM group only)
 
Weekly videos from study team
 
Self-weighing on digital scale
 
Other feedback
 
	
 
SMART goal setting
 
Help participant set a modest goal for exercise habit change
 

maintaining an active lifestyle. We will also include videos developed specifically for post-partum women on self, care, diet, and physical activity as appropriate. In order to address potential issues with access to availability of food and to increase the representation of diverse populations across the socioeconomic spectrum, all participants will be provided information on WIC access, local food banks, and other resources for healthy eating to address potential food insecurity. An outline of the weekly video emails is included in Table 1.

All participants will be scheduled for monthly individual visits with a member of the study team to discuss progress to date, potential barriers, and set goals for the upcoming month. During the first month, these visits will focus on self-care; in month 2, the focus will be dietary awareness; in month 3, participants will discuss physical activity with a member of the study team. A complete outline of the monthly phone calls is included in Table 2.

### a. Medically-Tailored Meal (MTM) Intervention

A standardized series of MTMs appropriate for women with GDM will be developed in partnership with Providence Community Kitchen chefs. Participants will receive 10 meals each week (5 lunch, 5 dinner) over the course of 12 weeks for a total of 120 meals. Meals will be designed to create a slight caloric deficit in order to promote gradual weight loss, but with sufficient energy intake and macronutrient balance to allow breastfeeding. These meals will be roughly 40% carbohydrate, 30% protein, and 30% fat in composition and will be consistent with recommendations from the American Diabetes Association for women who have been diagnosed with GDM. We will plan up to 20 unique lunch and dinner recipes for the series. Providence will prepare each meal to be between 450-600 kcal and to contain 6 ounces of protein, 4 ounces of vegetable and I cup of whole grain (at a minimum). An example menu of 10 meals (1 week) is included in Appendix A and an example of the nutritional information that will be provided with each meal is included in Appendix B. In addition to receiving the MTMs, participants will be advised to supplement their own breakfast +/- snacks to reach a total daily calorie goal determined by starting BMI category. Note that we will provide participants with lists of healthy, low-cost ADA compliant snacks and breakfast ideas that would meet the caloric requirements, so that they do no need to track calories on their own. We do not expect the women to keep track of calories, but rather are providing them with a meal structure that should help them remain within the designated calorie range for their BMI category. Using the snack lists plus consuming provided lunches and dinners, the daily dietary structure we will advise will include 5 eating episodes, structured as follows:

### BMI 30-39.9 – 1600 kcal daily (so long as breastmilk production not reduced)

- Breakfast 200-300 kcal
- Lunch (provided most days; on own 2d per week) 450-600 kcal
- Mid-Afternoon snack (on own) 100-200 kcal
- Dinner (provided most days; on own 2d per week) 450-600 kcal

### BMI 40-49.9 - 1800 kcal daily

- Breakfast 200-300 kcal
- Mid-morning snack: 200 kcal
- Lunch (provided most days) 450-600 kcal
- Mid-Afternoon snack (on own) 200 kcal
- Dinner (provided most days) 450-600 kcal

### BMI 50+ - 2000 kcal daily

- Breakfast 200-300 kcal
- Mid-morning snack: 200 kcal
- Lunch (provided most days) 450-600 kcal
- Mid-Afternoon snack (on own) 200 kcal

- Dinner (provided most days) 450-600 kcal
- After-dinner snack: 200 kcal

As described previously, study staff will run weekly EHR reports to identify when a participant is admitted to the hospital for delivery. About one week post-EDD, a member of the study team will contact the participant via text or phone call to ensure that she has delivered and is still planning to participate. We will coordinate with the participant and/or other household member to initiate home delivery of MTMs within 2 weeks (14 days) of delivery.

			Visit	
Primary Measures or Constructs	Screening	Baseline	Intervention	Follow-Up
Study evaluation of acceptability				х
Process measures				х
CGM		Х		х
Secondary Measures of Constructs				
Maternal and infant anthropometrics		х	х	х
Rapid Eating Assessment for Participants (REAP-S)		х		х
Food Insecurity		х		х
Awareness of GDM, management		х		
Diet-related comorbidities	х			
Infant feeding plans and practice		х		х
Financial stress		х		
Overall stress		х		
Confusion Hubub and Order Scale (CHAOS)		х		
Plans for weight-loss		х		
Health literacy		х	х	
Social support		Х		х
Data collection for recruitment and retention				
Pregnancy, delivery history		X		
OGTT	X			
Demographics		X		

Once per week, for a period of 3 months, 10 MTM (5 lunches and 5 dinners) portioned to feed one adult and frozen for ease of storage will be delivered directly to the participant's home by Providence Kitchen staff. MTM deliveries will include reheating instructions and recipe cards with nutritional information. During the monthly phone visits with a member of the study team, participants in the MTM treatment group will also be given the opportunity to provide feedback on the weekly meal delivery, food preparation, and troubleshoot any potential issues with this component of the intervention.

### b. Usual Care Comparison Group

As in the MTM group, participants will be contacted by a member of the study team via text or phone call to ensure that she has delivered and is still planning to participate before the email/phone visit schedule is initiated. The current standard of care for Wake Forest patients who had GDM during pregnancy includes no additional follow-up or intervention in the postpartum period. The monthly phone visits and weekly emails described above will therefore be significantly more intervention than they would normally receive. In addition, participants in the comparison group will receive written materials on self-care, nutrition, and exercise after pregnancy and community resources for healthy living. They will also receive specific information about following a diet consistent with recommendations from the American Diabetes Association for women who have been diagnosed with GDM, including forming their meals with roughly 40% carbohydrate, 30% protein, and 30% fat in composition and what their calorie goal should be for the day based on their BMI category. Participants in the comparison group will also receive the ADA placemat and electronic scale, as mentioned above.

Participants will receive \$50 and \$75 grocery store gift cards upon return of the CGM devices at the end of the first and second CGM data collection, respectively (\$125 total). Additionally, participants in the comparison

group will also receive 2 weeks (20 meals) of medically tailored meals from Providence Community Kitchen at the conclusion of their participation in the study. These meals will be delivered to the participant's home in a single delivery or will be available for pick-up.

### G. Measures

Measures in this study have been selected to reflect the feasibility, acceptability, and preliminary effectiveness objectives of this pilot study and include participant self-reported constructs, existing medical history and pregnancy history information from the EHR, and data collected directly via CGM. A table outlining the time points at which each measure is collected and the mode of collection is included in Table 3.

Demographics: We are collecting self-reported data on gender, race, ethnicity, highest level of education, marital status, and the number of adults and children living in the home.

Continuous Glucose Monitoring: Participants will wear a blinded FreeStyle Libre Pro CGM at baseline (first 2 weeks after delivery) and at follow up (after 3 months). CGM devices will be mailed to participants and a member of the study team will video call participants to provide instructions and real time guidance on attachment and activation of the CGM. In order to facilitate collecting baseline post-partum CGM data and weight, this call will occur as close to the actual date of delivery as is possible. The participants will wear the CGM for 14 days at the beginning (initial month) and end (3 months) of the study. They will also keep a daily diary of the timing of meals, sleeping, and exercise (Appendix C). Study staff will call participants on day 14 to remind them to remove the sensor and provide instructions and guidance if needed for removal. At the conclusion of the 3 months, an abbreviated remote virtual visit to aid in placement and activation of the second continuous glucose monitor will be conducted. Participants will return the continuous glucose monitors, readers, and daily diaries to the study coordinator by mail using prepaid mailers. A 1-page report with a summary of the 14-day glucose data (graph of glucose values with information on the normal range) will be provided back to participants together with a cover letter for them to share with their health care provider if they choose.

Table 4 shows the guideline-based CGM measures that we will analyze, using time in range 70-180 mg/dL, expecting that deviations in time in range will be lower both in duration and in amplitude for those with GDM than is typically seen in those with Type 2 Diabetes Mellitus. We will also investigate changes in glucose management indicator, an estimated measure of HbA1c from the CGM. We will also combine timestamped CGM data with diary responses about sleep and meal timing to describe: maximum postprandial glucose peak, steepness of glucose trajectories including increase and decrease, and nighttime hypoglycemic dipping during sleep and response to exercise.

During CGM wear time, participants will complete daily diaries documenting the timing of sleeping, waking, eating, and exercise. Only the time of the activity start will be recorded with no additional details. Start time of the CGM device will be recorded for the purpose of combining these data sources. These diaries were

unanimously considered easy to complete by participants in a previous study. The diaries will allow us to investigate additional diurnal glucose metrics that might be related more strongly to MTMs including postprandial glucose spikes, nocturnal dipping

Table 4.	. Standardized	CGM	Metrics	for	Clinical	Car	e

Measure	Explanation
Mean Glucose	
Glucose Management Indicator (GMI)	Roughly equivalent to HbA1c
Glycemic Variability (% coefficent of variation)	Target $\leq$ 36%
Time in range (%)	$70 \text{ mg/dL} \le \text{time} \le 180 \text{ mg/dL}$
Time above range (%)	180 mg/dL , time
Time below range (%)	Time < 70 mg/dL

during sleep, and response to exercise.

Anthropometrics: Maternal height, infant weight, and infant length will be collected from the EHR at baseline. Maternal weight will be collected within 2 weeks of delivery, at 2 months, and at 3 months using a digital scale mailed to the participant and facilitated by a member of the study team during the study telephone/virtual visit. In addition to collecting a maternal weight, participants will be provided instructions to weight their infant at the initial post-partum visit. We anticipate that some participants may not want to know their post-partum weight or could experience a negative emotional response to seeing that weight; therefore, participants will be provided with digital scales (BodyTrace) that will transmit weight data via cellular connection. These scales will transmit the data electronically to a digital platform (Carium) that will then provide aggregate data on all study participants to the study team. The display feature of the scale will be covered to prevent either the maternal weight or infant weight being displayed to the participant.

Medical History: Information on history of chronic diseases and other serious health conditions will be collected from the EHR in order to implement the eligibility criteria. Additionally, we will ask participants about their diagnosis of GDM during the current pregnancy, the strategies they may have employed to manage GDM, and their past pregnancy history.

Home environment: Participating women will complete the Confusion, Hubbub, and Order Scale (CHAOS). The CHAOS measure includes 15 items and is designed to capture environmental confusion in the home. In addition, participants will be asked to answer a series of questions about financial stress and food insecurity.

Dietary Habits and Quality: We will evaluate diet quality and dietary habits using a short, validated questionnaire, the Rapid Eating and Activity Assessment for Participants Short Version (REAP-S). The REAP-S was originally developed as a tool for primary care to providers rapidly assess and discuss nutrition and physical activity patterns with patients and consists of 16 questions and designed to focus making it more practical for use with low-literacy populations in clinical settings. The REAP-S can be used to quickly assess the relative intake of fat, cholesterol, fiber, sugar, and selected food groups.

Overall Stress: We will use the Stress Overload Scale-Short (SOS-S), a self-report measure that has demonstrated accuracy in identifying people who will develop stress-related pathology in the wake of stressful experiences. The SOS-S is also frequently used as a viable diagnostic tool for stress and stress-related disorders across diverse populations in the clinical setting.

Plans for Weight-Loss: We will collect a series of questions on satisfaction with weight-status, plans to lose weight post-partum, motivation level for weight-loss, and self-efficacy for weight-loss at baseline for all participants.

Health Literacy: We plan to use a series of single-item questions to assess confidence in filling out medical forms, frequency with which participants need help to read health information, and to rate their own reading ability. These questions have been validated for identifying patients with inadequate and marginal literacy in healthcare settings with limited time for administration.

We will also administer the Newest Vital Sign (NVS) to participating women as part of the monthly phone visit in month 2. The NVS is based on a nutrition label from an ice cream container and is designed to gauge ability to understand food labeling and nutrition literacy. Women will be provided the label via mail or email prior to the visit then asked 6 questions about it.

Social Support: We plan to collect the Lubben Social Network Scale (LSNS-6) to assess social support in study participants at both baseline and 3-months post-partum. Originally developed as a measure of social isolation in seniors, this measure has been previously validated in post-partum populations.

Process measures: In order to assess the feasibility of the MTM intervention, we will collect information from Providence Kitchen on the number of meals successfully delivered, the cost of meal preparation and meal delivery, any problems encountered with meal delivery, and nutritional information on the meals (kCal per meal, macronutrient composition and sodium content). In both treatment groups, we will assess the acceptability of other intervention components including the number of videos watched and the number of monthly phone visits completed. To assess the feasibility of CGM in this population, we will quantify the number of days the CGM was worn by each participant and collect data on any technical problems with the CGM devices or Adverse Events reported.

Study Evaluation: Follow-up data collection will also include a brief exit evaluation to determine general satisfaction/dissatisfaction with the MTM intervention, written/video education materials, CGM monitoring, and overall study experience.

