After enrollment, participants will be routinely monitored via the EHR to determine when they are admitted for delivery and to check for any potential problems during the delivery. To standardize anticipated contacts across all participants, the Estimated Date of Delivery (EDD) will be used to schedule meal deliveries, mailings, and email contacts for both treatment groups. Our plan is to initiate participant data collection post-partum within 2 weeks of delivery. Study staff will contact the participant approximately one week after the EDD to check on delivery status. We will also collect contact information during the enrollment process for an alternative contact person in

Table 1. Outline of Weekly Video Emails

Week	Video
1	The 4th Trimester (St. Louis Children's Hospital video)
2	HELP -Mindfulness
3	HELP - ABCs of emotions
4	Phone visit with study team (no email)
5	HELP - Tipping the calorie balance
6	HELP - Healthy Eating
7	HELP - More About Healthy Eating
8	Phone visit with study team (no email)
9	HELP - Physical Activity 101
10	HELP - Problem solving
11	HELP - Creating an environment for success
12	Phone visit with study team (no email)

the case of negative outcomes during or after delivery. Study staff will make at least five (5) attempts by phone, email, or text message to reach enrolled participants or their alternate contacts in the 2 weeks following the EDD. Continuous glucose monitors, readers, daily diaries, digital scales, and informational materials about the study and healthy diet resources will be delivered to participants by mail after the participant has been reached and continued participation is

confirmed. Those participants who do not respond to study contact after delivery

or who decline further participation will not receive study-related materials or meal delivery and will be considered as drop-outs. For those participants who are recruited and enrolled after giving birth, data collection will begin from the date of recruitment and informed consent.

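### The 14-day baseline CGM wear and the start of meals share the same 14 days after delivery, so the meal group's baseline can be partly on treatment and the exploratory CGM change diluted

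*Combined protocol and SAP*

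**What the plan says.** **First wear.** III.G (Continuous Glucose Monitoring) gives the timing twice: "Participants will wear a blinded FreeStyle Libre Pro CGM at baseline (first 2 weeks after delivery) and at follow up (after 3 months" and "The participants will wear the CGM for 14 days at the beginning (initial month) and end (3 months) of the study". On the placement call it adds that "this call will occur as close to the actual date of delivery as is possible".

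**Route to the first sensor.** III.E states: "Our plan is to initiate participant data collection post-partum within 2 weeks of delivery". It nevertheless anchors scheduling on the expected date: "the Estimated Date of Delivery (EDD) will be used to schedule meal deliveries, mailings, and email contacts for both treatment groups". It goes on: "Study staff will contact the participant approximately one week after the EDD to check on delivery status". Sensors and other materials are then "delivered to participants by mail after the participant has been reached and continued participation is" confirmed. Women enrolled after birth, eligible up to day 14, start data collection at consent. III.E also has staff watching the EHR for delivery admissions, and III.F.a describes a weekly report for this.

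**Meals.** III.F.a starts home delivery no later than day 14 after birth and supplies 10 meals a week for 12 weeks.

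**Second wear.** Beyond the two timing statements above, III.G says only: "At the conclusion of the 3 months, an abbreviated remote virtual visit to aid in placement and activation of the second continuous glucose monitor".

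**Use of the data.** Section II calls the 3-month CGM change primary within the second objective, preliminary effectiveness. III.H estimates change with mixed models and compares groups with t-tests; it has no rule for baseline days that fall after the first meal.

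**The concern.** A change from baseline measures the effect of meals only if the baseline precedes them. If meals begin while the first sensor is on, the MTM group's baseline moves towards its treated value and the comparison group's does not. The within-MTM change shrinks, and so does the contrast with the comparison group, if that group is recruited (III.E makes it conditional on time remaining).

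III.A describes the pilot as testing CGM for measuring glucose change associated with meals, and III.D says its estimates will help design a powered trial. A change diluted by scheduling would be a poor guide.

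The listed data may not allow a repair. The diary (III.G, Appendix C) records when a woman ate, not whether the meal was an MTM. The process measures list how many meals were delivered, not when.

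The second wear raises a related question: whether it falls during the meals, after them, or across both.

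**Working it through.** The plan gives no figure for this point, so there is nothing to reproduce. The check is a count of calendar days.

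**Inputs.** Day 0 is delivery; B is the first sensor day, M the first meal day, S the second sensor day. Each wear is 14 days (III.G). M is at most 14 (III.F.a). Meals last 12 × 7 = 84 days. Contact is at about EDD+7 (III.E). Mailing time is not given; 2–4 days is my assumption.

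**1. Baseline overlap.** Days in the meal period = max(0, min(B+14, M+84) − max(B, M)).

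- B = 0, M = 14: 14 − 14 = 0. This is the only pair with no overlap once M is at most 14.
- B = 0, M = 7: 14 − 7 = 7.
- B = 14, M = 14: 28 − 14 = 14.

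**2. The written route, delivery on the EDD.** Contact falls on day 7, so B is at least 7 even with no mailing time. With M = 14, overlap is 21 − 14 = 7 days; an earlier meal start or a later sensor gives more. The range is therefore 7–14 of 14.

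**3. With 2–4 days' mailing.** Contact day = 7 − (delivery day relative to EDD), and B = contact day + 2 to 4.

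| Delivery | B | Overlap, M = 14 | Overlap, M = 10 |
|---|---|---|---|
| EDD | 9–11 | 9–11 | 13–14 |
| EDD+5 | 4–6 | 4–6 | 8–10 |
| EDD+7 | 2–4 | 2–4 | 6–8 |

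Delivery at EDD−7 would put contact on day 14 and the sensor on days 16–18, outside the plan's own windows, so I claim nothing for it.

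**4. What overlap does to the change.** Let f be the on-meal fraction of the baseline wear. If the effect is immediate and constant, and the second wear is wholly on meals, the share left in the change is 1 − f: 0.71 at 4 days (1 − 4/14), 0.50 at 7 and 0.29 at 10. A slower onset dilutes less.

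**5. Second wear.** Days in the meal period = max(0, min(S+14, M+84) − S).

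| Meals from | S = 84 | S = 91 | S = 98 |
|---|---|---|---|
| Day 14 | 14 | 7 | 0 |
| Day 10 | 10 | 3 | 0 |
| Day 7 | 7 | 0 | 0 |

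Even on a fixed post-partum clock, the on-meal share varies with each woman's meal start. Only one of these nine cells is wholly on meals, so the condition in step 4 is a special case.

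The counts treat every day of the supply period as a meal day, although meals cover 5 lunches and 5 dinners a week.

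**The case against.** **Separate phases seem intended.** Table 3 marks CGM under Baseline and Follow-Up and not under Intervention, and Figure 1, the study schematic, may show an order. Read literally, the two windows can also fit with no overlap. This stands as far as it goes: a reader might infer that every MTM baseline is contaminated, and the documents do not show that. But a table of visits is not a timing rule, and the one clean combination conflicts with mailing sensors after contact at about EDD+7.

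**Contact could come earlier.** Delivery admissions are monitored, and III.G wants the placement call close to actual delivery. That is fair, and EDD+7 is one reading of the logistics. The text does not make the admission the trigger, however, and its scheduling anchor remains the EDD.

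**The 3-month origin can be worked out.** The social support measure is dated post-partum and shares the Follow-Up column with CGM. Delivery is the only anchor named in the maternal weight schedule. A reader might infer that the second wear has no determinable origin; that goes too far. A post-partum origin is inferable but unstated, and III.F.a applies a period of the same name to meal deliveries. Whether the wear is meant to be on or after meals stays open.

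**The stakes are limited.** The pilot is not powered for any effect (III.D), its analysis is deliberately limited (III.H), and the comparison group is conditional and not randomised. The uses of estimates that III.D spells out are retention, adherence, participation and accrual; carrying the CGM change forward is an inference from its more general sentence. This lowers the weight of the point without removing it.

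**Conclusion.** The concern holds in the readable text. The plan puts a 14-day baseline wear and the start of meals in the same 14 days and supplies sensors by a route that makes overlap likely. With delivery on the EDD and contact on day 7, at least 7 of the 14 baseline days fall in the meal period; this needs no mailing assumption. The larger counts rest on the assumed 2–4 days' mailing.

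The direction is clear: the MTM baseline is drawn towards its treated value. The size is not. It depends on actual dates and on how fast meals change glucose, which the documents do not give. A reader might take the shares in step 4 as expected losses, or infer a null or reversed result. Neither is supported: the shares need an immediate effect and a second wear wholly on meals, and a null or reversed contrast would need little carry-over and a mostly post-meal second wear.

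This should be fixed because it affects the CGM change named primary within the effectiveness objective and the listed data do not identify the affected days. Feasibility, acceptability and cost outcomes are untouched.

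**What to change.** The meal schedule is for the sponsor to decide; nothing here changes it.

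1. Reconcile the EDD scheduling in III.E with the wish in III.G to place the sensor close to actual delivery. Trigger contact and sensor mailing from the delivery found in the EHR monitoring already planned.
2. Record each woman's first and last meal-delivery dates; sensor dates are already collected. The last delivery does not mark the last meal eaten, because meals are frozen.
3. Report how many baseline and follow-up sensor days fall in the meal period. Pre-specify an analysis of CGM change using pre-meal baseline days, with a fixed minimum number of days and the same rule in both groups, alongside the full 14-day analysis.
4. State the origin of the 3-month point and whether the second wear is meant to be on or after meals, and interpret the estimate accordingly.

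**Cost.** Protocol wording, earlier calls and mailings, two dates per woman and no extra device. The pre-meal baseline is shorter, earlier post-partum, noisier and missing for some women, so it should sit beside the full baseline and not replace it.

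For scale, assume an EHR-report lag of 0–7 days and mailing of 2–4 days, giving 24 equally likely pairs and sensors on days 2–11. The proportion of women meeting the minimum is:

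| Minimum | Meals from day 14 | Day 10 | Day 7 |
|---|---|---|---|
| 3 days | 24/24 | 15/24 | 6/24 |
| 7 days | 15/24 | 3/24 | 0/24 |

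These are optimistic, since they leave out the time to reach each woman and schedule her call. Women who consent late after birth may have no pre-meal days. If days are independent (assumed), the day-sampling variance of the change relative to a 14-day baseline is (1/k + 1/14)/(2/14): 2.83 at k = 3 days and 1.50 at k = 7. With only 20 MTM women planned, a long minimum could lose most baselines.
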